4.4 Sample Size and Power

The sample size was calculated based on the mean difference in the cross-sectional area of the FSO by CT at Day 30 between the treatment and control sides from subjects in the PROGRESS study who underwent bilateral frontal BSD followed by unilateral placement of PROPEL Contour with the following assumptions:

- Expected mean difference of 9 mm² between the treatment and control sides
- A standard deviation (SD) of 18 mm² for side-to-side difference
- Target power of 95%
- Type I error rate of $\alpha = 0.05$, 2-sided

Internal, unpublished data suggest that SD = 18 is a reasonable assumption and that an achievable difference in mean cross-sectional areas of the FSO may be greater than 9 mm². The 9 mm² is deemed to be a clinically important difference to detect. Based on standard formulas for a t-test, a sample size of 56 subjects provides at least 95% power to detect a difference of 9 mm² in mean FSO cross-sectional area between treatment side and control side. Assuming up to 20% of subjects

with non-evaluable data on one or both sides, as it was reported in PROGRESS study report (R 28020), an additional 24 subjects will be enrolled for a total of 80 randomized subjects. Sample size calculations were carried out in PASS 14 (PASS 2015).

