6.3 Randomization

Following frontal BSD, eligible subjects will have their sinus sides randomly assigned to receive the PROPEL Contour (treatment) on one side, and no implant (control) on the contralateral side. The ratio of left to right sinus assignments will be 1:1. The randomization scheme will be generated by an independent statistician, and the randomization envelopes will be assembled by an in-house clinical research associate. The randomization scheme will be stratified by each clinical center, and will use permuted blocks of various sizes.

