9.3.3 Primary Analysis

The primary statistical method is a t-test comparing the mean FSO cross-sectional area at Day 45 in the treatment and control sides.

The study will be considered successful if there is a statistically significant difference in mean FSO cross-sectional area in favor of the treatment side. Although the alternative hypothesis is two-sided, only a statistically significant difference in average FSO area favoring the treatment side will constitute evidence of effectiveness.

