9.4.1 Multiplicity Adjustment for Key Secondary Endpoints

Intersect ENT intends to present inferential statistical results to support product labeling claims for 5 key secondary endpoints. This section describes the methods that will be used to control the familywise type 1 error rate (FWER) among the tests of these 5 secondary endpoints. All other secondary endpoints will be viewed as exploratory or explanatory in nature.

1. Cross-sectional area of the FSO change from baseline to Day 45 on CT by an independent, blinded reviewer
Test: $H_0: \mu = 0$ vs $\mu \neq 0$ by t-test
2. FSOT at Day 45 on CT by an independent, blinded reviewer
Test: $H_0: \mu = 0$ vs $\mu \neq 0$ by t-test
3. FSO minimum diameter at Day 45 on CT by an independent, blinded reviewer
Test: $H_0: \mu = 0$ vs $\mu \neq 0$ by t-test
4. Zinreich's modified Lund-Mackay score for frontal sinus at Day 45 on CT by an independent, blinded reviewer
Test: $H_0: \mu = 0$ vs $\mu \neq 0$ by t-test
5. Need for post-operative intervention by clinical investigators at Day 45

Test: $H_0: p_T = p_C$, where p_T and p_C are the probability of needing post-operative intervention on the treatment and control sides, respectively. Tested by McNemar's test (exact version).

Let $p_{(1)} \leq p_{(2)} \leq \dots \leq p_{(m)}$ be the $m=5$ p-values resulting from the above 5 tests, after being placed in ascending order. Adjusted p-values $\tilde{p}_{(1)}, \dots, \tilde{p}_{(m)}$ from Holm's step-down procedure will be calculated as follows:

$$\tilde{p}_{(i)} = \begin{cases} mp_{(1)} & \text{for } i = 1 \\ \max\left(\tilde{p}_{(i-1)}, (m-i+1)p_{(i)}\right) & \text{for } i = 2, \dots, m \end{cases}$$

Source: SAS Institute Inc. 2008. *SAS/STAT® 9.22 User's Guide*. Cary, NC: SAS Institute Inc., p 4839.

If any adjusted p-value exceeds 1, it is set to 1. Using this procedure, any adjusted p-value that is < 0.05 is statistically significant and supports a claim for the corresponding endpoint, while any

CONFIDENTIAL

25 of 33

May not be reproduced outside of Intersect ENT without written permission from Document Control

adjusted p-value ≥ 0.05 is not statistically significant. Both adjusted and unadjusted p-values will be reported.

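### The primary t-test omits the implanted side (left or right) that the trial randomises; a pre-specified side term would be a cheap, minor gain in precision

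*SAP*

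**What the plan says.** SAP 6.3 fixes the allocation: "The ratio of left to right sinus assignments will be 1:1", in permuted blocks of varying size, stratified by centre. Protocol 18.1 agrees. The randomised groups are therefore implant-left and implant-right.

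SAP 9.3.1 takes each subject's treatment-minus-control difference in Day 45 area and averages it over the ITT population. SAP 9.3.3 gives the test: "The primary statistical method is a t-test comparing the mean FSO cross-sectional area at Day 45 in the treatment and control sides". It does not say that the test is paired, but SAP 4.4, 9.3.1 and 9.3.2 all work with the within-subject difference, and I read it so.

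Implanted side is absent from the primary analysis, from the sensitivity analyses (9.3.4) and from the subgroups (9.3.5). The only planned check on whether the difference varies is by site (6.10). SAP 9.4.1 plans t-tests, also without a side term, for four of the five key secondary endpoints, including "FSO minimum diameter at Day 45 on CT by an independent, blinded reviewer".

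**The concern.** Blocking on left versus right is there so that a systematic difference between the two sides cancels. Let D be the mean left-minus-right area without an implant, from whatever cause. The treatment-minus-control difference is then raised by D in implant-left subjects and lowered by D in implant-right subjects. A one-sample t-test on the pooled differences treats those two shifts as scatter, so the reported standard error is larger than the design warrants. The cancellation in the estimate is also incomplete when evaluable subjects are not split evenly. That is likely here: 80 subjects over up to 20 sites is about four per site, so blocks will often be unfinished, and up to 20% of subjects are assumed non-evaluable.

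At stake are the width of the confidence interval and some power, mainly if the true effect is below the design value. Precision matters somewhat more for the key secondary endpoints, because Holm's first step tests at 0.05/5 = 0.01.

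**Working it through.** **The plan's own figure.** SAP 4.4 uses "Expected mean difference of 9 mm² between the treatment and control sides", "A standard deviation (SD) of 18 mm² for side-to-side difference", two-sided alpha 0.05 and 95% power. A one-sample t-test on differences with effect size 9/18 = 0.5 needs 54 subjects (noncentral t). At 56 the power is 95.7%, so the statement that "a sample size of 56 subjects provides at least 95% power to detect a difference of 9 mm²" is met. With 80 randomised and 20% lost, 80 × 0.80 = 64 are evaluable and power is 97.6%.

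**Formulas.** Let n be the evaluable number, b = (n_left − n_right)/n, and σ² the residual variance.
- Difference: δ + D for implant-left, δ − D for implant-right.
- Total variance near balance: σ² + D². SD 18 was set for treatment-minus-control differences, so I take it as the total: σ² = 324 − D².
- Unadjusted estimate: conditional shift D·b; true variance σ²/n + D²·Var(b). Its reported SE is about √(324/n).
- Adjusted estimate (mean of the two group means, pooled variance, n − 2 df): SE = σ/√(n(1 − b²)), with no shift from b.

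**Assumptions not in the documents.** D = 0, 4.5 or 9 mm²; blocks of 2, 4 and 6; 20 sites of 4; 16 of 80 lost at random. Simulated under these, b has an SD of about 7.6%, so Var(b) = 0.076² = 0.0058. Across the set-ups tried, the SD of b is about 6 to 8%.

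**True variance, n = 64.**
- D = 4.5: unadjusted 303.75/64 + 20.25 × 0.0058 = 4.746 + 0.117 = 4.863 (SD 2.21). Adjusted about 4.746 × 1.0058 = 4.774 (SD 2.18). Fall: 1 − 4.774/4.863 = 1.8%.
- D = 9: unadjusted 243/64 + 81 × 0.0058 = 3.797 + 0.470 = 4.267 (SD 2.07). Adjusted about 3.797 × 1.0058 = 3.819 (SD 1.95). Fall: 10.5%; 4.267/3.819 = 1.117, or about 12% more information.

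**Simulation (20,000 trials per D).** Empirical SDs of the two estimates were 2.21 and 2.19 at D = 4.5, and 2.06 and 1.95 at D = 9, in line with the formulas.

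| D (mm²) | Mean reported SE, unadjusted → adjusted | Type I error, unadjusted | Power at true 6 mm² |
|---|---|---|---|
| 0 | 2.24 → 2.25 | about 5% | about 75%, no gain |
| 4.5 | 2.24 → 2.17 | 4.4–4.8% | 75% → 77% |
| 9 | 2.25 → 1.95 | 3–3.6% | 76% → 86% |

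The adjusted test holds its nominal level within simulation error. At the design effect of 9 mm², simulated power goes from 97.8% to 98.2% (D = 4.5) or from 98.4% to 99.5% (D = 9).

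**Chance shift in the estimate.** One SD of b moves it by 4.5 × 0.076 = 0.34 mm² or 9 × 0.076 = 0.68 mm². A 36/28 split at D = 9 moves it by 9 × 8/64 = 1.1 mm².

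**Break-even.** The reported interval narrows once D exceeds about 1.5 mm². The true variance falls once D²·Var(b) > (324 − D²)/64 × Var(b), that is D² > 324/65 = 4.98, or D above about 2.2 mm².

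**The case against.** A paired t-test is a valid and conventional analysis for this design, and nothing in the documents suggests that left and right ostia differ on average. Every subject must have disease on both sides and a successful dilation of both. D = 9 mm² equals the whole difference that SAP 4.4 calls clinically important, so it is an extreme case. Any D² is probably already inside the SD of 18, and the 80 enrolled leave a margin over the 56 needed. With fewer, larger sites the imbalance is smaller: at an imbalance SD of 6% and D = 9, (3.797 + 81 × 0.0036)/(3.797 × 1.0036) = 1.073, a gain of about 7%. All of this stands, and it keeps the point minor. It does not explain why the factor that the blocking balances is left out of the analysis.

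Three stronger readings are tempting, and the documents support none of them.
- **Bias or false positives.** A reader might infer that the result is biased or its type I error inflated. The shift averages zero if losses do not depend on side, and the unadjusted test errs on the conservative side.
- **A large gain in information.** Squaring the ratio of reported standard errors at D = 9, (2.25/1.95)² = 1.33, suggests 33%. Most of that comes from the unadjusted SE overstating the true SD (2.25 against 2.06). The real gain is about 12%.
- **Removal of all asymmetry, on every endpoint.** Only the population-average difference can be removed; each subject's own asymmetry stays in the error term. Key secondary 1 is a change from baseline, so it already removes a stable anatomical difference.

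**Conclusion.** The point holds as a minor, inexpensive improvement. The planned test is valid, and the sample size of 56 evaluable subjects need not change. Without a side term, an average left-right difference stays in the error variance and, when the evaluable groups are unequal, leaves a small chance shift in the estimate. With a total SD of 18, 64 evaluable subjects and the assumed site and block structure, the benefit is nil at D = 0, slight at D = 4.5 and moderate at D = 9. Because power at 9 mm² is already about 97.6%, the gain on the primary endpoint is mainly a narrower reported interval; power gains appear only if the true effect is smaller than planned. The direction follows from the design, but the size rests on D, which the documents do not give. No size was computed for the key secondary endpoints.

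**What to change.** In SAP 9.3.3, specify a linear model of the Day 45 treatment-minus-control difference on an implanted-side term coded +1 for left and −1 for right. Test the intercept on n − 2 degrees of freedom. With that coding the intercept is the plain average of the two group means; the term should not be re-centred at its sample mean, because the intercept would then return to the unadjusted mean. Keep the plain paired t-test as a supporting result.

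In SAP 9.4.1, use the same model for the t-tests of key secondaries 2 to 4 (FSOT volume, FSO minimum diameter, Zinreich score). For key secondary 1 the benefit is limited to left-right differences that arise at or after dilation.

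Make the change before the unblinding for the Day 45 primary analysis (SAP 5.2); an analysis designed after database lock would be post hoc under SAP 6.1. The cost is a sentence or two in the SAP, one degree of freedom, and an interval about 0.3% wider if D is zero. No new data are needed, since the assigned side is known for every randomised subject.

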9.3.4 Sensitivity Analyses

Sensitivity analysis for medical or surgical intervention

Because intervention with oral steroids or surgical intervention may confound the primary efficacy endpoint, the following method will be applied to the analyses in cases where such interventions are performed:

- If a subject initiates oral steroids or undergoes revision ESS for CRS conditions attributable to the FSO/frontal recess before Day 45, this represents treatment failure. If the intervention occurs on the treatment side or both sides, the FSO cross-sectional area of the treatment side will be imputed with the value of the control side (i.e., side-to-side difference in FSO area is

zero). If the intervention occurs on the control side only, the FSO cross-sectional area in the control side will be imputed as zero (i.e., totally occluded).

- If a patient initiates oral steroids for other reasons not involving the FSO/frontal recess before Day 45, this does not represent treatment failure. In this scenario, the side-to-side difference in FSO cross-sectional area for that subject will be imputed as zero.
- No other data imputation rules will be applied in the planned statistical analyses.

Sensitivity analysis for missing data

Subjects with a missed visit, lost to follow-up, or with FSO cross-sectional area ‘unable to view’ by the independent, blinded reviewer will be considered as missing data. If more than 10% of the primary efficacy data are missing, the following imputation analyses will be performed to test the robustness of the primary efficacy conclusion in order:

- *Worst-case imputation.* The worst case of side-to-side difference in FSO area is zero. If the primary efficacy endpoint passes (p -value < 0.05) using worst-case imputation, then there is no need to do a best-case imputation analysis.
- *Best-case imputation.* The best case of side-to-side difference in FSO area is equal to the average for the treatment site.

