All statistical tests will be two-sided and interpreted at a 5% significance level. A p-value < 0.05 will be considered statistically significant. Unless stated otherwise, a two-sided 95% CI will be calculated and presented.

All available data at each time point will be presented. No imputations for missing data are planned, unless indicated otherwise.

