6.7 Missing Data for Efficacy and Safety Endpoints

Missing data for each efficacy endpoint will be handled as described in Sections 9.1 and 9.3.4.

For continuous endpoints, change from baseline will be set to missing at visits with missing postbaseline values or where data were imputed to missing. Continuous efficacy endpoints will be set to missing for subjects who received any of the following not allowed medication post-baseline procedure:

- Corticosteroids (e.g., oral, parenteral or injection, budesonide or other sinus steroid irrigations/rinses or drops, breath powered Xhance, nebulized steroids administered nasally or other drug eluting stents) through Day 45; or
- Biologics for CRS treatment (e.g., Dupixent).

For binary endpoints, subjects with missing efficacy data, early withdrawals, and/or subjects who received not allowed corticosteroids or biologics for chronic sinusitis condition attributable to the FSO/frontal recess will be imputed as a treatment failure. If a subject initiates high-dose steroid for other reasons not involving FSO/frontal recess, this does not represent treatment failure.

Additional rules for handling of missing data and rescue treatments are detailed below:

- *Missing efficacy data.* Visits with missing data (due to a missed visit or missing component of a composite endpoint) will be set to treatment failure.
- *Early withdrawals.* Only visits following the early withdrawal visit will be set to treatment failure.
- *Rescue treatments.* Subjects who rescue with corticosteroids (before Day 45) or biologics will be set to treatment failure at all subsequent visits and continuous endpoints set to missing.
- *Missing baseline value.* For efficacy endpoints, a missing value at baseline will not be imputed, and the endpoint will be set to missing for all visits.

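### Day 45 areas that SAP 6.7 sets to missing are not in the count behind the 10% missing-data trigger in 9.3.4, and those removed for non-oral steroids or biologics are filled by neither sensitivity analysis.

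*SAP*

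**What the plan says.** The primary endpoint is one number per subject: treatment-side minus control-side FSO area at Day 45, averaged over the ITT population (SAP 9.3.1) and tested with a t-test (9.3.3). Section 6.1 plans no imputation unless stated otherwise.

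Section 6.7 removes some observed values: "Continuous efficacy endpoints will be set to missing for subjects who received any of the following not allowed medication post-baseline procedure". The medications are corticosteroids through Day 45 (oral, parenteral or injected, sinus irrigations or drops, Xhance, nebulised, other drug-eluting stents) and biologics for CRS. It also blanks an efficacy endpoint at every visit when the baseline value is missing. It refers the reader to 9.1 and 9.3.4 for the handling of missing data.

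Section 9.3.4 has two parts.

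- **Intervention analysis, no trigger.** For oral steroids or revision ESS for a frontal cause before Day 45, the difference becomes zero if the treatment side or both sides are affected. If only the control side is affected, the control area becomes zero. For oral steroids given for another reason, the difference becomes zero. The part closes by ruling out any further imputation rules.
- **Missing-data analysis, with a trigger.** The definition opens "Subjects with a missed visit, lost to follow-up, or with FSO cross-sectional area" and ends with the reviewer being unable to view the area. The next sentence is the trigger: "If more than 10% of the primary efficacy data are missing, the following imputation analyses will be performed". The worst case fills a difference of zero.

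**The concern.** A subject whose area is blanked by 6.7 is as absent from the primary t-test as one who missed the visit, yet 6.7 cases are not in the definition that feeds the trigger. The intervention analysis picks up oral steroids only. A subject given an injection, steroid rinse or drops, Xhance, a nebulised steroid, another drug-eluting stent or a biologic therefore drops out of the primary test and is reached by neither sensitivity analysis.

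These absences are unlikely to be random. Protocol 15.1 allows the barred corticosteroids before Day 45 when frontal inflammation rises or persists and the subject has symptoms. At stake are whether a missing-data check runs at all, and how much of the ITT population it covers when it does.

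**Working it through.** **Inputs.** From SAP 4.4: "Expected mean difference of 9 mm² between the treatment and control sides"; "A standard deviation (SD) of 18 mm² for side-to-side difference"; 95% target power; 56 evaluable and 80 randomized subjects; up to 20% of subjects "with non-evaluable data on one or both sides". From 6.1: "All statistical tests will be two-sided and interpreted at a 5% significance level". From 9.3.4: the trigger is more than 10%, and the worst-case fill is 0. I take all 80 randomized subjects as ITT. The documents give no split of missingness by reason, so the rates and counts in steps 3 and 4 are assumptions.

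**1. The plan's own figure.** For a paired t-test with effect 9/18 = 0.5, two-sided 0.05, noncentral t: power is 94.7% at n = 53, 95.0% at n = 54 and 95.7% at n = 56. The statement that 56 gives at least 95% is reproduced.

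**2. Trigger.** 10% of 80 is 8, so more than 10% means at least 9 subjects.

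**3. What the literal list lets through.** Take 8 listed subjects (8/80 = 10.0%, trigger not met) and K more removed by 6.7 for non-oral reasons.

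| K | Absent from t-test | Share of 80 | n in t-test | Check runs on literal list | Check runs if 6.7 cases count |
|---|---|---|---|---|---|
| 1 | 9 | 11.25% | 71 | no | yes |
| 4 | 12 | 15% | 68 | no | yes |
| 8 | 16 | 20% | 64 | no | yes |
| 16 | 24 | 30% | 56 | no | yes |

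The K = 8 row equals the 20% non-evaluable allowance in 4.4. Power at n = 64 is still 97.6%, so the matter is coverage and robustness, not power.

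**4. Chance that the trigger is missed.** P(X ≤ 8), X binomial with 80 subjects and an assumed listed rate:

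| Listed rate | P(trigger missed) |
|---|---|
| 6% | 95% |
| 8% | 81% |
| 10% | 59% |
| 15% | 13% |
| 20% | 1% |

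**5. What including everyone does under the existing zero fill.** Observed n = 64, mean 9, SD 18; 16 zeros added.

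- Mean = 64 × 9 / 80 = 7.2 mm², a fall of 20%.
- SD = √[(63 × 18² + 64 × 9² − 80 × 7.2²)/79] = √(21,448.8/79) = 16.48.
- t = 7.2/(16.48/√80) = 3.91, p = 0.0002. Before the fill, t = 9/(18/√64) = 4.00, p = 0.0002.
- Nearer the threshold, with the same 16 zeros: p = 0.0200 becomes 0.0203 (mean 5.37 to 4.30), and p = 0.0490 becomes 0.0492 (mean 4.52 to 3.61).

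Adding zeros lowers the mean and the standard error almost in proportion, so the estimate moves and the test hardly does.

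**The case against.** The best counter-argument is that 9.3.4 never says its list is exhaustive. A value that 6.7 has set to missing fits the ordinary sense of missing primary data, and 6.7 itself points to 9.3.4. A sensible analyst might count these cases. That reading is possible, but the definition stands directly before the trigger and omits them. Two analysts could reach different counts, and the count decides whether the check runs.

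Three stronger readings are tempting, and the documents do not support them.

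- *Nothing removed by 6.7 is ever filled.* Oral-steroid users before Day 45 are filled by the intervention analysis whether or not the trigger is met. Their problem is different: 6.7 says missing, 9.3.4 gives a value, and neither says which applies in which analysis.
- *The gap can decide the trial.* The planned worst case is zero, and step 5 shows that zeros leave the p-value essentially where it was. Uncounted subjects could overturn a result only if their true differences favoured control, and neither planned imputation would reveal that.
- *The 10% might be counted by side.* 9.3.1 defines one difference per subject, 9.3.4 speaks of subjects, and both of its fills are set on the difference. The unit is the subject.

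It is also fair that at a listed rate of 20%, the upper limit of the overall allowance in 4.4, the trigger would almost always be met. Non-oral 6.7 cases would then still be outside the list of subjects to be filled.

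**Conclusion.** The point holds as a gap in coverage and a conflict between two sections. As written, the check can stay off with 20% of ITT subjects absent from the primary test (8 listed plus 8 removed by 6.7 for non-oral reasons), or run on only part of the gap. The likelihood depends on an assumed listed rate and runs from 95% at 6% to 1% at 20%. The number removed by 6.7 for non-oral reasons is not given anywhere and may be small.

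The consequence is an understated extent of missingness and a sensitivity estimate that is too favourable or never produced: 9.0 against 7.2 mm² when 16 of 80 are filled at zero, assuming an observed mean of 9 and SD of 18. It is not a threat to the significance test under the planned fill. The change should be made before the blind is broken for the primary analysis.

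**What to change.** In SAP 9.3.4, replace the definition and trigger with text to this effect:

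- Every ITT subject who contributes no observed Day 45 side-to-side difference to the primary t-test, for any reason including Section 6.7, counts as missing, one count per subject.
- If more than 10% of ITT subjects are missing by this count, all of them enter the imputation analyses, except that subjects covered by the oral-steroid/revision-ESS rule keep the value that rule assigns. No subject is then imputed in two ways.
- State whether 6.7 or 9.3.4 governs those subjects in the primary analysis.
- Report the number missing by reason.

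The cost is a few lines of SAP text and one derived flag, with no change to data collection, sample size or the primary test. The downside is that the check will run more often and its estimate will be less favourable. The p-value under the zero fill will barely change, so the gain is complete coverage and an honest estimate, not a more demanding test.

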9.3.1 Definition

The cross-sectional area will be determined by the independent, blinded reviewer on CT at Day 45 within the mucosa at the location of the measured minimum diameter between 5 mm superior and 5 mm inferior to the ostium. It will be reported in mm² for the left and right ostia separately.

For each subject, the difference between FSO cross-sectional area at Day 45 in the treatment and control sides will be calculated and then averaged across all subjects in the ITT population. The FSO cross-sectional area will be set as missing if the FSO is unable to be viewed or measured.

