9.3.2 Statistical Hypothesis

The primary efficacy hypothesis is that the placement of the PROPEL Contour will significantly increase the FSO cross-sectional area on the treatment side versus the control side. The relevant null and alternative hypotheses for this primary efficacy endpoint are:

$$H_0: \mu = 0$$

$$H_1: \mu \neq 0$$

Where μ represents the mean difference between the treatment and control sides in cross-sectional area of the FSO at Day 45.

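### The 'worst-case' fill for missing Day 45 area differences is a constant equal to the null value, so its p < 0.05 check can hardly disagree with the primary test and can pass a fragile result as robust.

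*SAP*

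**What the plan says.** SAP 9.3.1 defines the endpoint within subject: "the difference between FSO cross-sectional area at Day 45 in the treatment and control sides will be calculated and then averaged across all subjects". It adds: "The FSO cross-sectional area will be set as missing if the FSO is unable to be viewed or measured". SAP 9.3.2 tests whether μ is zero, where μ "represents the mean difference between the treatment and control sides in cross-sectional area of the FSO at Day 45". By SAP 6.1, missing data are not imputed unless a section says otherwise.

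SAP 9.3.4 says otherwise when more than 10% of the primary data are missing. Imputation analyses are then run in order "to test the robustness of the primary efficacy conclusion":

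- Worst case: "The worst case of side-to-side difference in FSO area is zero".
- Gate: if the endpoint reaches p < 0.05 "using worst-case imputation, then there is no need to do a best-case imputation analysis".
- Best case: "The best case of side-to-side difference in FSO area is equal to the average for the treatment site".

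SAP 4.4 allows for up to 20% non-evaluable subjects, twice the trigger, so these analyses may well be needed.

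**The concern.** A worst-case analysis should ask whether the conclusion survives missing outcomes that go against the implant. Zero says only that the implant did nothing in the missing subjects, although an individual difference can be negative. The value is also entered as an exact constant, so the filled data set has less spread than real subjects would show.

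No other rule closes the gap. SAP 6.7 classes missed visits as treatment failure but attaches no area to that; in the rescue rules of 9.3.4, failure of the treatment side or of both sides again means a difference of zero. The only fully occluded value in 9.3.4 is assigned to the control side. Of the three methods in SAP 9.1, observed-case leaves values missing, non-responder imputation is for binary measures, and last observation carried forward has no scheduled post-baseline CT before Day 45 to carry. SAP 10.2 compares baseline characteristics and post-baseline events, stratifies by method and timing of assessment, and refers back to 6.7, but supplies no unfavourable area.

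At stake is the statement in the report: a significant primary result could be called robust to missing data after a check that could hardly have said anything else.

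**Working it through.** **Inputs.** Mean difference 9 mm², SD of the difference 18 mm², two-sided α 0.05, N = 80 (SAP 4.4); null value 0 (9.3.2). The cases are 9 missing (11.25%, the smallest count above 10%), 16 missing (20%) and, for reference, 24 missing (30%, above the plan's allowance, which leaves the 56 evaluable subjects of 4.4).

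**Paired reading.** SAP 9.3.3 says only t-test. The definition of μ and the SD in 4.4 imply a one-sample test on differences, and the sample size agrees: noncentral-t power is 95.02% at n = 54 and 95.7% at n = 56, so the stated 56 does give at least 95%. A two-sample test with the same SD would need 104 per group.

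**Zero below the mean.** P(difference < 0) = Φ(−9/18) = 0.309, if normal.

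**Constant fill.** With n observed (mean m, SD s) and N − n values set to d:

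- mean′ = [nm + (N − n)d]/N
- Var′ = [(n − 1)s² + nm² + (N − n)d² − N·mean′²]/(N − 1)
- t′ = mean′/√(Var′/N), on N − 1 df

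When d = 0, the sum and the sum of squares of the differences do not change.

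*Design effect, 16 missing (n = 64, m = 9).* Observed: SE = 18/8 = 2.25, t = 4.00. Filled: mean 576/80 = 7.20; sum of squares 63×324 + 64×81 = 25,596; Var′ = (25,596 − 80×51.84)/79 = 271.5, so SD 16.48 and SE 1.842; t = 3.91. The mean falls to 80% of its value and the SE to 82%.

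*Borderline, 16 missing (m = 4.61).* Observed: t = 4.61/2.25 = 2.049, p = 0.0446. Filled: mean 3.688, SD 16.18, t = 2.039, p = 0.0448.

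**Same mean of zero, with variance.** Multiple imputation of the difference (proper normal draws, no covariates, Rubin's rules with small-sample df), with the missing-subject mean set to 0 in the borderline case: estimate about 3.69, SE about 2.27, t about 1.62, p about 0.11. Zero as a mean does test something. Zero as a constant does not.

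**When can the check disagree with the primary test, and what would a real stress test show?** The last two columns are at the design effect (observed mean 9).

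| Missing | Observed p at which zero fill gives exactly 0.05 | Constant fill that tips p to 0.05 (mm²) | Missing-subject mean that tips it, multiple imputation (mm²) |
|---|---|---|---|
| 9 | 0.0499 | −29.6 | −26.8 |
| 16 | 0.0498 | −15.1 | −11.5 |
| 24 | 0.0497 | −8.4 | −4.1 |

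Zero fill reverses a significant result only if the observed p lies between the second column and 0.05. In simulation (200,000 trials per setting; true means 0, 3, 4.5, 6 and 9; 9, 16 and 24 missing), 99.5% to 100% of significant primary results also passed zero fill, and no non-significant result became significant.

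**A fragile pass.** With observed p = 0.04 and 16 missing, zero fill gives 0.0402 and passes. Significance is lost once the constant falls below about −0.8 mm².

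**Best-case step, read as the mean difference.** Filling with m keeps the mean and shrinks the SD to 18√[(n − 1)/79]. With 16 missing, m = 3.577 has observed t = 1.590 and p = 0.117; the filled SD is 16.07 and t = 1.990, p = 0.05. With 9 missing the corresponding observed p is 0.082.

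**The case against.** Zero is a recognisable conservative assumption for a superiority claim: no benefit in anyone unobserved. It matches the plan's own rule for a failed treatment side. It also pulls the estimate down, from 9 to 7.2 mm² with 16 missing, so the analysis has content. At the design effect a proper analysis agrees with it: the missing subjects would need a mean near −12 mm² to overturn the result, and SAP 4.4 expects that the true difference may exceed 9. A missed visit removes both sides of the subject, which weakens any link between loss and side-specific outcome. On this view only the label is wrong.

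Most of this stands, and it limits the point to smaller effects or heavier loss. It does not rescue the p < 0.05 criterion, which is what the SAP uses to judge robustness and to decide whether to go further.

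Two stronger readings are tempting. The first is that the null value alone makes the check empty. The 0.11 above shows that it does not: the cause is the null value together with a constant that has no variance. The second is that closed ostia are being lost as missing data. The documents do not show this. Whether a closed ostium is scored 0 mm² or set to missing depends on the radiographic protocol CP-00038, which is not among them.

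**Conclusion.** The point holds in this form: the zero fill is not a worst case, and its p < 0.05 check cannot serve the purpose that 9.3.4 states. The check can differ from the primary verdict only for observed p of 0.0499 to 0.05 (9 missing) or 0.0498 to 0.05 (16 missing). These figures assume a paired t-test and an SD of 18 mm²; the imputation figures and the 31% also assume normal differences.

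A reader might infer that the trial could succeed on imputed data. It cannot: SAP 9.3.3 ties success to the primary t-test alone. Nor do the figures suggest that a result at the planned effect would be fragile.

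The best-case step is a side issue. The gate means it runs essentially only after a non-significant primary result, where it can only help. Its wording is ambiguous: the sentence is about a difference, but SAP 6.2 uses 'treatment site' for the treated side. Reading it as the treated-side mean area would need areas that the documents do not give, so no conclusion is drawn from that reading.

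The change is worth making before the primary analysis, but it is a correction to a supporting analysis and does not challenge the primary one.

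**What to change.** In SAP 9.3.4:

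1. Rename the zero fill a no-effect imputation. Report its estimate and interval, but do not use its p < 0.05 as evidence of robustness or as the gate to the best-case step.
2. Add one delta-adjusted (tipping-point) multiple imputation of the side-to-side difference that keeps full between-subject variance. Shift the imputed differences against the implant in fixed steps until p reaches 0.05, and report the tipping value whatever the primary result. If p is already 0.05 or more with no shift, say so.
3. Limit the shifts to differences compatible with areas of at least 0 mm². Where the control-side area is observed, the lower limit is minus that area; where both sides are missing, state how the limit is set.
4. Screening core-lab areas may be used as predictors; this is optional. The 10% trigger can stay.
5. If the best-case step is kept, state that its fill is the mean side-to-side difference, and do not present it as a robustness test.

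The cost is a short SAP revision and modest programming. No change is needed to the primary test, sample size or data collection. The drawback for the sponsor is a sensitivity result that may look less favourable.
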